**Table 6 - Tusamitamab raptansine dose reduction criteria**

Actual dose level	Dose level interval
Starting dose (100 mg/m  )	>90 mg/m 
Dose level -1 (80 mg/m  )	>72.5 mg/m  and ≤90 mg/m 
Low dose	>0 mg/m  and ≤72.5 mg/m 

- Dose delay: A dose will be considered as delayed if the tusamitamab raptansine administration date of the current cycle - 14 days - tusamitamab raptansine administration date of the previous cycle is >2 days. Dose delay is not defined for the first cycle.
- Dose omission is defined as a dose not administered at the scheduled visit but administered afterwards.
- Dose interruption: a dose will be considered to be interrupted if the tusamitamab raptansine administration is stopped during an infusion regardless of whether it is restarted or not.

Dose modifications and dose interruptions will be analyzed by participant and cycle as follows:

- **Participant** (number of participants treated will be used as denominator)
  - Number (%) of participants with at least 1 dose modification
    - Number (%) of participants with at least 1 dose delayed
    - Number (%) of participants with at least 1 dose reduction
    - Number (%) of participants with at least 1 dose omission
    - Number (%) of participants with at least 1 dose interruption
- **Cycle** (number of cycles started will be used as denominator)
  - Number (%) of cycles with at least 1 dose modification
    - Number (%) of cycles with at least 1 dose delayed
    - Number (%) of cycles with at least 1 dose reduction
    - Number (%) of cycles with at least 1 dose omission
    - Number (%) of cycles with at least 1 dose interruption

#### **4.7.1.3 Ramucirumab exposure**

The dose information will be assessed by the following:

- Total number of cycles started.
- Number of cycles started per participant.
- Duration of ramucirumab exposure (in weeks) is defined by (date of last administration of ramucirumab + 14 days - date of first administration of ramucirumab)/7.
- Actual dose (in mg/kg). In case of dose interruption, actual dose will be the sum of the actual doses administered before and after the dose interruption.

- Cumulative dose (in mg/kg): the cumulative dose is the sum of all actual doses of ramucirumab, given from first to last administration.
- Actual dose intensity (ADI in mg/kg/week): defined as the cumulative dose divided by the duration of ramucirumab exposure (in weeks).
- Planned dose intensity (PDI in mg/kg/week): corresponds to the planned dose multiplied by the theoretical total number of doses started and divided by the theoretical cycle duration expressed in weeks (ie, 2 weeks per cycle started).
- Relative dose intensity (RDI, in %):  $100 \times \frac{\text{ADI (mg/kg/week)}}{\text{PDI (mg/kg/week)}}$ .

The total number of cycles started, and the number of cycles started by participant will be summarized as a quantitative variable and by category (number [%] of participants receiving at least 1 cycle, at least 2 cycles, etc) Duration of ramucirumab exposure, cumulative dose, ADI and RDI will be summarized quantitatively.

The following variables will be derived to describe dose modifications and dose interruptions:

- Dose reduction: The first administration will not be counted as a dose reduction. For the second and subsequent ramucirumab administrations, dose reduction will be determined using the dose level intervals provided in [Table 7](#), by comparing the current dose level to the previous dose level. If the current dose level is below the dose level interval of the previous dose administration, then the current dose level is considered reduced.

**Table 7 - Ramucirumab dose reduction criteria**

Actual dose level	Dose level interval
Starting dose (8 mg/kg)	>7 mg/kg
Dose level -1 (6 mg/kg)	>5.5 mg/kg and $\leq$ 7 mg/kg
Dose level -2 (5 mg/kg)	>4 mg/kg and $\leq$ 5.5 mg/kg
Low dose	>0 mg/kg and $\leq$ 4 mg/kg

- Dose delay: A dose will be considered as delayed if the ramucirumab administration date of the current cycle - 14 days - ramucirumab administration date of the previous cycle is  $>2$  days. Dose delay is not defined for the first cycle.
- Dose omission is defined as a dose not administered at the scheduled visit but administered afterwards at a subsequent scheduled visit.
- Dose interruption: A dose will be considered to be interrupted if the ramucirumab administration is stopped during an infusion regardless of whether it is restarted or not.

Dose modifications and dose interruptions will be analyzed by participant and cycle as follows:

- **Participant** (number of participants treated will be used as denominator)
  - Number (%) of participants with at least 1 dose modification
  - Number (%) of participants with at least 1 dose delayed

- Number (%) of participants with at least 1 dose reduction
- Number (%) of participants with at least 1 dose omission
- Number (%) of participants with at least 1 dose interruption
- **Cycle** (number of cycles started will be used as denominator)
  - Number (%) of cycles with at least 1 dose modification
    - Number (%) of cycles with at least 1 dose delayed
    - Number (%) of cycles with at least 1 dose reduction
    - Number (%) of cycles with at least 1 dose omission
  - Number (%) of cycles with at least 1 dose interruption

#### **4.7.2 Adverse events**

##### **General common rules for adverse events**

All AEs will be graded according to National Cancer Institute Common Terminology for Adverse Events (NCI-CTCAE version 5.0) and coded to a lower-level term (LLT), preferred term (PT), high-level term (HLT), high-level group term (HLGT), and associated primary system organ class (SOC) using the Medical Dictionary for Regulatory Activities (MedDRA) version currently in effect at Sanofi at the time of database lock.

The AEs will be analyzed in the following 3 categories:

- Pre-treatment AEs: AEs that developed, worsened or became serious during the pre-treatment period.
- Treatment-emergent adverse events (TEAEs): AEs that developed, worsened or became serious during the treatment-emergent period.
- Post-treatment AEs: AEs that developed, worsened or became serious during the post-treatment period.

Similarly, the deaths will be analyzed in the pre-treatment, treatment-emergent, and post-treatment periods.

The primary AE analyses will be on TEAEs. Pre-treatment AEs and post-treatment AEs will be described separately.

An AE with incomplete or missing date/time of onset (occurrence, worsening, or becoming serious) will be classified as a TEAE unless there is definitive information to determine it is a pre-treatment or a post-treatment AE.

If the assessment of the relationship to IMP is missing for an AE, this AE will be assumed as related to IMP. Missing grade will be left as missing.

Multiple occurrences of the same event in the same participant will be counted only once in the tables within a treatment phase, using the maximum (worst) grade by treatment phase. Summaries will be provided for all grades combined and for Grade  $\geq 3$  (including Grade 5). Missing grades, if any, will be included in the “all grades” category.

The AE tables will be sorted as indicated in [Table 8](#).

**Table 8 - Sorting of AE tables**

AE presentation	Sorting rules
SOC, HLGT, HLT and PT	By the internationally agreed SOC order and by alphabetic order of HLGTs, HLTs and PTs
SOC and PT	By the internationally agreed SOC order and decreasing frequency of PTs a, b
SMQ/CMQ and PT	By decreasing frequency of SMQs/CMQs and PTs a
PT	By decreasing frequency of PTs a

a Sorting will be based on the experimental intervention arm at the highest dose.

b The table of all TEAEs presented by SOC and PT will define the presentation order for all other tables (eg, treatment-emergent SAE) presented by primary SOC and PT, unless otherwise specified.

### **Analysis of all adverse events**

The overview of TEAE with the details below will be generated:

- Any TEAE
- Any Grade  $\geq 3$  TEAE
- Grade 5 TEAE (any TEAE with a fatal outcome during the treatment-emergent period)
- Any treatment-emergent SAE
- Any treatment-emergent AESI
- Any TEAE leading to permanent full study intervention discontinuation
- Any TEAE leading to permanent partial discontinuation of tusamitamab ravtansine
- Any TEAE leading to permanent partial discontinuation of ramucirumab
- Any TEAE related to IMP
- Any Grade  $\geq 3$  TEAE related to IMP
- Any treatment-emergent SAE related to IMP
- Any treatment-emergent corneal event (CMQ “Corneal events compound level”)
- Any treatment-emergent peripheral neuropathy event TEAE (SMQ “Peripheral neuropathy” [Narrow and Broad])
- Any ocular/visual symptoms TEAE (CMQ “Eye disorders exclude corneal disorders”)

The AE summaries of [Table 9](#) will be generated with number (%) of participants experiencing at least one event. The analyses will be performed for all grades combined and for grades  $\geq 3$ .

**Table 9 - Analyses of adverse events**

Type of AE	MedDRA levels
All TEAE	Primary SOC, HLGT, HLT, and PT
	Primary SOC and PT
	PT
TEAE related to IMP as per Investigator's judgment	Primary SOC and PT
TEAE related to tusamitamab raptansine as per Investigator's judgment	Primary SOC and PT
TEAE related to ramucirumab as per Investigator's judgment	Primary SOC and PT
Treatment-emergent SAE	Primary SOC, HLGT, HLT and PT
	Primary SOC and PT
Treatment-emergent SAE related to IMP as per Investigator's judgment	Primary SOC and PT
Treatment-emergent SAE related to tusamitamab raptansine as per Investigator's judgment	Primary SOC and PT
Treatment-emergent SAE related to ramucirumab as per Investigator's judgment	Primary SOC and PT
TEAE leading to permanent full study intervention discontinuation	Primary SOC and PT
TEAE leading to permanent partial discontinuation of tusamitamab raptansine	Primary SOC and PT
TEAE leading to permanent partial discontinuation of ramucirumab	Primary SOC and PT
TEAE leading to death (death as an outcome of the AE as reported by the Investigator in the AE page)	Primary SOC and PT
TEAE related to tusamitamab raptansine and leading to death (death as an outcome of the AE as reported by the Investigator in the AE page)	Primary SOC and PT
Pre-treatment AE	Overview a
Pre-treatment SAE	Primary SOC and PT
Post-treatment AE	Overview a
Post-treatment SAE	Primary SOC and PT
TEAE leading to dose modification of tusamitamab raptansine (including dose delay, dose reduction and dose omission)	Primary SOC and PT
TEAE leading to dose modification of ramucirumab (including dose delay, dose reduction and dose omission)	Primary SOC and PT
TEAE leading to dose interruption of tusamitamab raptansine	Primary SOC and PT
TEAE leading to dose interruption of ramucirumab	Primary SOC and PT

a Will include the following AE categories: any AEs, any serious AEs, any AEs leading to death, any AEs (except for pretreatment AEs) leading to permanent full study intervention discontinuation.

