- **Analysis of secondary efficacy endpoints for the doublet cohort:**

- Duration of response will be summarized for the subgroup of participants who achieve confirmed objective response in the all-treated population with descriptive statistics using Kaplan-Meier methods. The median DOR and associated 95% CI will be provided.
- Progression-free survival will be summarized using Kaplan-Meier methods. The median PFS times and associated 95% CI will be provided, along with probabilities of being progression-free at different time points.
- Disease control rate (DCR) will be summarized using descriptive statistics and 95% exact confidence intervals (CIs) will be provided using the Clopper-Pearson method.

- **Analysis of secondary efficacy endpoints for the triplet cohort:**

- ORR will be summarized using descriptive statistics and 95% exact confidence intervals (CIs) will be provided using the Clopper-Pearson method.

- **Analysis of safety endpoints:**

- Number and percentage of participants experiencing TEAEs by primary system organ class (SOC) and preferred term (PT) will be summarized by NCI-CTCAE V5.0 Grade (all grades, and Grade ≥ 3) for the all-treated population. Similar summaries will be prepared for treatment-related TEAEs, TEAEs leading to definitive discontinuation, TEAEs leading to dose modification, serious TEAEs, TEAEs with fatal outcome, adverse events of special interest (AESIs), and AEs/SAEs occurring during the post-treatment period. In addition, the number (%) of participants with any Grade 5 AE (TEAE and post-treatment) will be summarized.
- Hematology and clinical chemistry results will be graded according to the NCI-CTCAE V5.0, when applicable. Number and percentage of participants with laboratory abnormalities (all grades and by grade) using the worst grade during the treatment period will be provided for the all-treated population.

Data Monitoring Committee: No

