1.3 SCHEDULE OF ACTIVITIES (SOA)

1.3.1 Study flow chart - Doublet cohort

Procedure	Pre-screening ^a	Screening ^b	Treatment cycle 1		Treatment cycle 2 +		End of treatment	90 (± 7) Days (3 month) Follow-up ^d	Notes*
Day		Days to first infusion	D1		14 (± 2) days from previous infusion		30 (± 5) days from last infusion		
			Pre-infusion ^c	EOI	Pre-infusion ^c	Every 8 weeks (± 7 days)			
CEACAM5 expression status ^a (archival or fresh tumor tissue) – central IHC/ prescreening Informed consent	X								
Informed Consent		X							
Inclusion/exclusion criteria		≤ 28	X						Section 5.1, 5.2
Demography, medical/surgical/disease/smoking history ^e		≤ 28							
NSCLC characteristics ^f	X	≤ 28							
Height		≤ 7							
Performance status (ECOG)		≤ 7	X		X		X	X	Section 8.2.1, 8.2.3
Physical examination, including vital signs, body weight ^g		≤ 7	X		X		X	X	Section 8.2.1
Hematology ^h		≤ 7	X		X		X		Section 8.2.5, 10.2 (Appendix 2)
Coagulation ⁱ		≤ 7	X		X		X		Section 10.2, (Appendix 2)
Clinical blood chemistry ^j		≤ 7	X		X		X		Section 8.2.5, 10.2 (Appendix 2)
Urinalysis ^k		≤ 7	X		X				Section 10.2, (Appendix 2)
HBsAg & HCV serology and HIV test (only if required at country level)		X							Section 10.8, (Appendix 8)

Procedure	Pre-screening ^a	Screening ^b	Treatment cycle 1		Treatment cycle 2 +		End of treatment	90 (± 7) Days (3 month) Follow-up ^d	Notes*
Day		Days to first infusion	D1		14 (± 2) days from previous infusion		30 (± 5) days from last infusion		
			Pre-infusion ^c	EOI	Pre-infusion ^c	Every 8 weeks (± 7 days)			
Urine or Serum pregnancy test ^l		≤ 7			X		X	X	Section 10.2 (Appendix 2) Section 10.5 (Appendix 5)
Left ventricular ejection fraction (MUGA/echocardiogram) ^m		≤ 28							Section 8.2.4.2
12-lead ECG ⁿ		≤ 7	X	X	X		X		Section 8.2.4.1
Specific ocular tests ^o		≤ 28					X		Section 8.2.2
Tusamitamab rvtansine/Ramucirumab administration			X		X				Section 6.1
AE assessment ^p	X		Continuously throughout the study period						Section 8.2, 8.3, 10.3 (Appendix 3)
Concomitant medication ^q		X	Continuously throughout the study period						Section 6.5
Tumor assessment – RECIST v1.1 - CT/MRI; relevant surrogate markers ^r		≤ 28				X	X	X	Section 8.1
Circulating CEA ^s	X	≤ 28				X	X	X	
IgG			X						
Record further anticancer therapy								X	
Tusamitamab rvtansine and ramucirumab PK			Refer to PK/ATA flowchart, Section 1.3.3						Section 8.5
Tusamitamab rvtansine Immunogenicity			Refer to PK/ATA flowchart, Section 1.3.3						Section 8.9

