9.4.2.2 Analysis of adverse events

Adverse events will be collected from the time prescreening informed consent is signed until at least 30 days after the last infusion of the study treatment. All AEs will be categorized according to NCI-CTCAE V5.0 and classified by system organ class (SOC)/ preferred term (PT) according to the latest available version of the MedDRA dictionary.

- Prescreening AEs are defined as AEs occurring during the prescreening period.
- Screening AEs are defined as any AEs occurring during the screening period.
- Treatment-emergent AEs are defined as AEs that develop, worsen (according to the Investigator's opinion), or become serious during the treatment period.
- Post-treatment AEs are defined as AEs that are reported during the post-treatment period.

The NCI-CTCAE grade will be taken into account in the summary. For participants with multiple occurrences of the same PT, the maximum grade will be used.

The primary focus of AE reporting will be on TEAEs. Pre-screening, screening and post-treatment AEs will be described separately.

Treatment-emergent adverse events:

An overall summary of TEAEs will be provided. The number and percentage of participants experiencing any of the following will be provided:

- TEAEs
- Grade ≥ 3 TEAEs
- Grade 5 TEAEs (any TEAE with a fatal outcome during the treatment period)
- Serious TEAEs
- TEAEs leading to definitive treatment discontinuation
- Treatment-related TEAEs
- Treatment-related TEAEs Grade ≥ 3

- Serious treatment-related TEAEs
- AESI

Number and percentage of participants experiencing TEAEs by primary SOC and PT will be summarized by NCI-CTCAE V5.0 grade (all grades and Grade ≥ 3) for the all-treated population. Similar summaries will be prepared for treatment-related TEAEs, TEAEs leading to definitive discontinuation, TEAEs leading to dose modification, serious TEAEs, TEAEs with fatal outcome, AESIs, and AEs/SAEs occurring during the post-treatment period. In addition, the number (%) of participants with any Grade 5 AE (TEAE and post-treatment) will be summarized.

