#### *Observation period*

The observation period will be divided into 4 segments:

- The **pretreatment period** is defined as the period up to the first IMP administration.
  - The **prescreening period** is defined as the period from the pre-screening informed consent or addendum to informed consent (for participants with available CEACAM5 result) to the day before the screening informed consent.
  - The **screening period** is defined as the period from the screening informed consent up to the first IMP administration.
- The **on-treatment period** (ie, **treatment-emergent period**) is defined as the period from the first IMP administration to the last IMP administration + 30 days.
- The **posttreatment period** is defined as the period from the end of the on-treatment period.

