## Analysis of adverse events of special interest (AESIs) and other AEs of interest

Adverse events of special interest (AESIs) will be defined using eCRF and other AEs of interest will be selected for analyses as indicated in [Table 10](#). Number (%) of participants experiencing at least 1 TEAE will be provided overall for AESI, and for each other event of interest, by SOC and PT (if applicable). The DLTs observed during the DLT-observation period will be listed in the DLT-evaluable population. Tables will be sorted as indicated in [Table 8](#).

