### **Analyses according to potentially clinically significant abnormalities (PCSA) and NCI grading**

For laboratory variables, analyses according to NCI grading will be made based on NCI-CTCAE Version 5.0. In addition, for laboratory variables for which the NCI-CTCAE scale is not applicable, such as vital signs and ECG variables, PCSA analyses will be performed based on the PCSA list currently in effect at Sanofi at the time of the database lock.

Analyses according to PCSA and NCI grading will be performed based on the worst value during the treatment-emergent period, using all measurements (either local or central, either scheduled, nonscheduled or repeated).

QTcF prolongation will be graded according to NCI-CTCAE version 5.0. The frequency of participants each grade of QTcF prolongation during the on-treatment period will be summarized. For participants with multiple occurrences of QTcF prolongation during the treatment, the maximum grade per participant will be used.

For laboratory variables, vital signs and ECG variables above, the incidence of participants with at least one PCSA during the treatment-emergent period will be summarized regardless of the baseline level and according to the following baseline status categories:

- Normal/missing
- Abnormal according to PCSA criterion or criteria

The number (%) of participants with QTcF abnormality worsening during the on-treatment period (worst value per participant) will be displayed.

For laboratory variables graded by NCI-CTCAE,

- The number (%) of participants with abnormal laboratory tests at baseline will be presented by grade.
- The number (%) of participants with an abnormal laboratory test during the treatment-emergent period will be summarized by grade. When appropriate, the number (%) of participants with abnormality of any grade and with Grade 3-4 abnormalities will be provided.
- For liver function test abnormalities, the baseline status will be provided according to multiples of the upper limit of normal (ULN) for each test.

For laboratory variables graded neither by NCI-CTCAE nor by PCSA, the number (%) of participants with laboratory test results outside normal ranges will be provided.

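### SAP Table 9 gives post-treatment AEs a four-category overview where the protocol calls for SOC/PT summaries, so late non-serious, non-fatal AEs are counted but not named (minor)

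*SAP*

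**What the plan says.** Protocol Section 9.4.2.2 sets the reference format: participants with TEAEs, as number and percentage, by primary SOC and PT, for all grades and for Grade 3 or higher, in the all-treated population. The next sentence extends similar summaries to a list of other event classes that ends with "AESIs, and AEs/SAEs occurring during the post-treatment period". The synopsis carries the same list, ending "adverse events of special interest (AESIs), and AEs/SAEs occurring during the post-treatment period".

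SAP Section 4.7.2, Table 9, has two post-treatment rows. Post-treatment SAEs are tabulated by primary SOC and PT. Post-treatment AEs get an overview, which the footnote limits to "any AEs, any serious AEs, any AEs leading to death, any AEs (except for pretreatment AEs) leading to permanent full study intervention discontinuation". The text introducing the table says "The analyses will be performed for all grades combined and for grades" 3 or higher, so the overview has a grade split but no preferred term.

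Three other SAP statements matter:
- For AESIs and other events of interest: "Number (%) of participants experiencing at least 1 TEAE will be provided overall for AESI".
- For laboratory and ECG data: "Analyses according to PCSA and NCI grading will be performed based on the worst value during the treatment-emergent period".
- The on-treatment period "is defined as the period from the first IMP administration to the last IMP administration + 30 days".

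**The concern.** The protocol names AEs and SAEs together and gives them the same kind of table. The SAP splits them and drops the preferred term for AEs. SAP v2.0 is stated to follow amended protocol 02, yet its table of major changes neither records nor explains this departure.

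The data exist. Protocol Sections 4.1 and 8.3.2 and the doublet flow chart (footnote d) require new IMP-related AEs arising in follow-up to be followed until they resolve or stabilize. Protocol Section 8.3.1 makes conduction defects and Grade 3 or higher liver enzyme increases AESIs whether or not they are serious. AE incidence is a secondary endpoint for a new combination. What is at stake is whether a reader of the study tables can tell which late, non-serious toxicities occurred, or only how many participants had one.

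**Working it through.** The check is a comparison of text. The plan gives no figure to reproduce.

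**Step 1. Which events are post-treatment.** SAP Section 4.7.2 counts an AE as post-treatment if it developed, worsened or became serious after the treatment-emergent period. That period closes 30 days after the last IMP administration. Protocol Section 9.4.2 uses the same boundary.

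**Step 2. Where a preferred term appears for an event after day 30.**

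| Event after day 30 | Named by PT? | Source |
|---|---|---|
| Serious | Yes | SAP Table 9, post-treatment SAE row |
| Fatal, with AE as cause of death | Yes | SAP Section 4.7.2, analysis of deaths |
| Grade 4 AST/ALT increase | Yes, because it must be reported as an SAE | Protocol Appendix 2, Table 18, note a |
| Eye event | Possibly | SAP Section 4.7.2, ocular-symptom and corneal occurrence outputs, not all with a stated time window |
| Other non-serious, non-fatal AE | No | SAP Table 9 overview only |

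An event in the last row enters the any-AE line of the overview, and rarely the discontinuation line. Neither line carries a term. If an AE began on treatment and worsened after day 30, its term appears in the TEAE tables at the on-treatment grade, but the later worsening is not named.

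**Step 3. Whether another output fills the gap.** The AESI and events-of-interest tables are written for TEAEs. The laboratory and ECG grade tables use the worst treatment-emergent value. The eDISH-like liver plot states no time window and might show a late value, but it names no AE. The post-treatment overview has no AESI line.

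**Step 4. Whether a scheduled visit can produce such an event.** The doublet flow chart sets the end-of-treatment visit at "30 (± 5) days from last infusion".
- Earliest day: 30 − 5 = 25. Latest day: 30 + 5 = 35.
- Treatment-emergent period ends: day 30.
- Permitted visit days after that boundary: 31 to 35.

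Chemistry is scheduled at this visit. A Grade 3 AST/ALT rise first seen on days 31 to 35, if not serious, therefore falls outside both the TEAE tables and the laboratory grade tables. For ECGs the opening is narrower: footnote n limits the end-of-treatment ECG to days 22 to 30, and the 90-day visit has no scheduled ECG or chemistry. A late conduction defect would come to light only through an unscheduled test.

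**Step 5. Size.** The documents give no rate of late non-serious AEs. For illustration only, assume that 2% to 10% of the 30 to 36 treated participants (SAP Section 1.1) have one: 30 × 0.02 = 0.6 to 36 × 0.10 = 3.6 participants. The range has no anchor in the documents and shows only the order of magnitude.

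**The case against.** The case for leaving Table 9 alone has three parts.

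First, Protocol Section 9.4 calls itself a summary and leaves detail to the SAP. Section 9.4.2.2 puts the main focus on TEAEs and says post-treatment AEs are described separately. Similar does not mean identical. This allows some latitude in layout, but not enough to drop the preferred term. The sentence before fixes the format as SOC and PT by grade, the list names AEs beside SAEs, and the SAP itself treats an overview and an SOC/PT table as different outputs.

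Second, Protocol Section 8.3.2 requires collection of all AEs only until at least 30 days after the last dose. For new events after that, the protocol centres on IMP-related AEs, SAEs and AESIs. An SOC/PT table of all post-treatment AEs would mix related events with an incomplete set of unrelated ones, and its percentages would need care. This stands as a limit on interpretation. The SAP does not offer it as a reason for the overview, and a table note deals with it.

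Third, a late Grade 3 liver enzyme increase or conduction defect is an AESI and must reach the sponsor within 24 hours. This stands too. A reader might infer that late toxicities would go unnoticed, but the documents do not support that: the gap is in tabulation, not in safety reporting.

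**Conclusion.** The mismatch holds. The SAP departs without explanation from a commitment that the protocol makes twice. The events affected are non-serious, non-fatal AEs that develop or worsen after day 30, apart from some eye events that other outputs may show.

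The impact is minor. Few events are expected, the study is descriptive, and neither the primary endpoints nor the dose decision changes. This rests on two readings: that the protocol's similar summaries include SOC and PT, and that the SAP text specifies every AE summary table to be produced. It applies to the doublet cohort, the only cohort the SAP covers.

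A reader might draw a larger effect from the calendar. Five of the 11 permitted end-of-treatment days (45%) fall after day 30, and days 31 to 90 are 60 of the 90 days (67%) to the safety visit. Neither figure measures impact, since both count days rather than visits or events. The end-of-treatment visit is also brought forward if another anticancer therapy is about to start (Protocol Sections 1.1, 4.1 and 7), so 5/11 is not the share of visits held after day 30.

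**What to change.** In SAP Table 9, change the entry for post-treatment AEs to overview plus primary SOC and PT, for all grades and Grade 3 or higher. Add a note that unrelated non-serious AEs are not systematically collected after day 30. If the sponsor prefers to keep the overview alone, the SAP should state the departure from Protocol Section 9.4.2.2 and give the reason. An AESI line in the post-treatment overview would be a useful option.

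The cost is a wording change and one short table, built from AE data already collected and MedDRA-coded. No new data collection is needed.
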